7.2.1 MEDuI Determination

Participants will return to the study site 16 to 24 hrs later for erythema response evaluation. Each will be questioned non-directively to assess compliance with the requirements of the protocol and to identify changes in health/concomitant medications. Any changes/AEs will be recorded in source documentation. All

participants will acclimate at room temperature for 10 minutes prior to response evaluation (as described in SOP PPD).

A trained evaluator will grade the responses of the UV exposed sites, under warm white fluorescent or tungsten illumination of at least 450 lux, using the grading scale shown in Table 8. Grades will be recorded, along with any comments, in source documentation and the evaluator will time stamp the evaluation completion.

Table 8. Grading Scale for Erythema Responses

0	No erythema response
1	Minimally perceptible erythema with no clearly defined borders
2	Perceptible erythema with clearly defined borders (covering more than 50% of the exposure site)
3	Moderate erythema with sharp borders*
4	Dark red erythema with sharp borders*
5	Dark red erythema with sharp borders and possible edema*
6	Intense erythema with sharp borders and edema*

* If moderate, dark red or intense erythema does not reach borders of exposed site, an explanation will be provided in the source documentation.

The MEDuI is defined as the first exposure site in the series with erythema □□□□□ H.

Participants whose MEDuI can be determined will continue with study procedures. Participants whose MEDuI cannot be determined will be discontinued.

The progression of erythema grades must be consistent with the UV doses administered.

Participants with pronounced tanning responses are not considered good candidates for SPF studies with an erythema endpoint. They should be discontinued from the study and another participant should be added.

To facilitate study scheduling, participants may leave the study site after MEDuI determination and return up to 1 week later to resume study procedures. Re-scheduled participants whose testing has been paused will be questioned non-directively on their return to assess compliance with the requirements of the protocol and to identify changes in health/concomitant medications. to confirm ongoing qualification. Any changes/AEs will be recorded in source documentation.

7.2.2 Application of Study Treatments

7.2.2.1 SPF Standard Application

The study technician will apply 80 ± 2 mg ($2.0\text{mg}/\text{cm}^2 \pm 0.05 \text{ mg}/\text{cm}^2$) of the SPF standard to its assigned test site using a fingercot. A double-weighing procedure (weighing the syringe/pipette + product + fingercot, prior to and after application) to ensure the required quantity of SPF standard is delivered. Using the fingercot and light pressure, the SPF standard will be evenly spread over the test site; spreading time will be 35 ± 15 secs, depending on the ease of application.

7.2.2.2 Test Product Application

The study technician will apply 80 ± 2 mg ($2.0\text{mg}/\text{cm}^2 \pm 0.05 \text{ mg}/\text{cm}^2$) of the test product using a fingercot. A double-weighing procedure (weighing boat + product + fingercot, prior to and after application) to ensure the required quantity of product is delivered. Using the fingercot and light pressure, the test product will be evenly spread over the test site; spreading time will be 35 ± 15 secs, depending on the ease of application.

7.2.2.3 Additional Application Instructions for All Test Materials

- The study technician will ensure test materials are homogenous (thoroughly mixed and/or shaken well) prior to application
- Test sites may be cleaned using a dry cotton pad or equivalent prior to test material application.
- Evenness of application will be verified by observation with a Woods Lamp. If non-uniformity or streaking of the test material is noted, the test site shall be rejected and may not be used for testing. If another test site is available, re-application of the test material should be attempted.
- Test material dispensing (test site allocation, weight (mg), spreading time, drying time) will be recorded in source documentation.
- Wait at least 15 mins after applying the test materials before commencing UV irradiation of unprotected and protected sites.

7.2.4 UV Doses for Unprotected and Protected Sites

7.2.4.1 Repeat Unprotected Minimal Erythema Dose (MEDuR) Determination

A series of 5 (timed) UV doses, increasing by 25 percent increments (J/m^2) across the 5 subsites, will be administered to the assigned unprotected test site of the back. The UV exposure selected for each subsite will be based on the previous MEDuI evaluation, which appears as the  point, as shown above in Section 7.1.2, Table 6.

Immediate Response Codes and procedural information will be recorded in source documentation as described in Section 7.1.2, Table 7.

7.2.4.2 Protected Minimal Erythema Dose (tpMEDp/ssMEDp) Determination

A series of 5 (timed) UV doses, increasing by 25 percent increments (J/m^2) across the 5 subsites, will be administered to each protected test site (i.e., the sites treated with SPF standard [ssMEDp] and test products [tpMEDp]). The UV exposure selected for each subsite will be determined by the previously determined MEDuI and the expected SPF of the test materials, as shown in Table 9.

Table 9. FDA Final Rule Dose Series

Expected SPF	Multiple of expected SPF and Participant MEDuI				
< 8	0.64	0.80	1.00	1.25	1.56
> 8 to 15	0.69	0.83	1.00	1.20	1.44
> 15	0.76	0.87	1.00	1.15	1.32

Immediate Response Codes and procedural information will be recorded in source documentation as described in Section 7.1.2.

While administering treatment evaluation UV doses for any Model 16S (single port) testing, as required, the technician may adopt the following procedure to accommodate participant scheduling needs.

- Reduce the test material UV exposure times by the correct UV dose series multiplier and immediately continue UV exposures.

Management approval to adopt this approach and the outcome will be recorded in source documentation.

Participants will be instructed to avoid UV exposure; they will be reminded of the study requirements/lifestyle considerations and asked to return to the study site 16 to 24 hrs after completion of Day H UV doses.

7.3 Day 3

7.3.1 MEDuR, ssMEDp and tpMEDp Determination

Participants will return to the study site 16 to 24 hrs later for erythema response evaluation. Each will be questioned non-directively to assess compliance with the requirements of the protocol and to identify changes in health/concomitant medications. Any changes/AEs will be recorded in source documentation. All participants will acclimate at room temperature for 10 minutes prior to response evaluation (as described in SOP PPD).

A trained blinded evaluator will grade the responses of the UV exposed sites, under warm white fluorescent or tungsten illumination of at least 450 lux, using the grading scale shown in Table 8. Grades will be recorded, along with any comments, in source documentation and the blinded evaluator will time stamp the evaluation completion.

Note: the same blinded evaluator should evaluate erythema response throughout the study.

MED (MEDuR, ssMEDp and tpMEDp) is defined as the first exposure site in the series □□□□□□□□□□□□□□□ Hs Erythema grades, comments and the evaluation completion time stamp will be recorded in source documentation.

Photographs of the test sites, which do not reveal participant identity, may be taken to document unexpected results and/or AEs.

8.0 Statistical Analysis

Statistical analyses will be performed by PPD using Microsoft Excel 365 (2021). Since all methodologies for the summary and statistical analyses of the data collected in this study are specified in the protocol, a separate Reporting Analysis Plan (RAP) will not be created. Any major modification of the analysis plan will be documented as a protocol amendment.

8.1 Analysis Population

The analysis population will include all eligible participants (qualified based on the inclusion/exclusion criteria) who are randomized, received study treatment and provide valid results.

8.2 Participant Disposition and Demography

Participant disposition and demographic characteristics will be tabulated and presented with summary descriptive statistics (sample size, mean, standard deviation, median, minimum and maximum) for continuous variables (e.g., age) and frequency distributions for categorical variables (e.g., sex).

8.4 Summary Analyses

Calculations and statistical analyses will be performed in compliance with the FDA Final Rule (2011) [1] and reviewed by PPD Quality Assurance. Individual participant results will be tabulated along with summary statistics, including mean SPF, valid test data used in the SPF calculations, SD, SE and t-value (as described in Section 8.3). Passed or failed grades will also be listed, along with excluded participants and reasons for exclusion.

9.0 Rejected Test Data:

9.1 Invalid Data

Test data are deemed invalid and shall be excluded under the following circumstances:

- Erythema is not present on either the unprotected or protected test site(s).
- Erythema is present at all subsites on either the unprotected or protected test site(s).
- The responses are inconsistent with the series of UV doses administered.

Data from a maximum of three participants per test material may be invalidated for the above reasons.[1]

9.2 Other Reasons for Data Rejection

Test data may be excluded for other reasons, examples include:

- Participant was non-compliant with study protocol
- Participant lost to follow up
- Participant unable to complete the study
- Participant discontinued due to an AE
- Participant disqualified due to an administrative/technical failure
- Participant dismissed due to product wash off
- Participant discontinued/withdrawn (See Section 5.4)

10.0 Adverse Events

The safety population is defined as all randomized participants who received at least one dose of a study treatment.

The PI, or designated designee(s), is responsible for detecting, documenting and reporting events that meet the definition of an AE or SAE.

The PI, or designated designee(s), is responsible for following up serious AEs (SAEs); AEs considered to be test product (or study procedure) related; and AEs that caused the participant to discontinue or be withdrawn from the study.

10.1 Definition of an Adverse Event (AE)

An AE is any untoward medical occurrence in a clinical study participant, temporally associated with the use of a test product, whether or not considered related to the test product. An AE can therefore be any unfavorable and unintended sign (including an abnormal laboratory finding), symptom, or disease (new or exacerbated) temporally associated with the use of a test product.

Events Meeting the AE Definition:

- Unexpected or unusual reactions which occur within a test site that cannot be completely described by the scale in Table 8 (e.g., hives) will be recorded as AEs.
- Any abnormal laboratory test results (hematology, clinical chemistry, or urinalysis) or other safety assessments (e.g., ECG, radiological scans, vital sign measurements), including those that worsen after test product administration, considered clinically significant in the medical and scientific judgment of the PI or medically qualified designee (i.e., not related to progression of underlying disease).
- Exacerbation of a chronic or intermittent pre-existing condition including either an increase in frequency and/or intensity of the condition after test product administration.
- New conditions detected or diagnosed after test product administration, even though it may have been present before the start of the study.
- Signs, symptoms, or the clinical sequelae of a suspected drug-drug interaction.
- Signs, symptoms, or the clinical sequelae of a suspected overdose of either test product or a concomitant medication. Overdose per se will not be reported as an AE/SAE unless it is an intentional overdose taken with possible suicidal/self-harming intent. Such overdoses should be reported regardless of sequelae.
- Lack of efficacy per se will not be reported as an AE. Such instances will be captured in the efficacy assessments. However, the signs, symptoms, and/or clinical sequelae resulting from lack of efficacy will be reported as AE if they fulfill the definition of an AE.

Events NOT meeting the AE definition:

- Any clinically significant abnormal laboratory findings (if applicable) or other abnormal safety assessments which are associated with an underlying disease, unless judged by the PI, or medically qualified designee, to be more severe than expected for the participant's condition.
- A medical or surgical procedure (e.g., endoscopy, appendectomy) is not an AE. The condition that leads to the procedure is the AE (e.g., gastritis, appendicitis).
- Situations where an untoward medical occurrence did not occur (social and/or convenience admission to a hospital).
- Anticipated day-to-day fluctuations in a pre-existing disease/condition present or detected at the start of the study that did not worsen.
- Localized erythema caused by exposure of the skin to UV radiation is expected and will not be reported as an adverse event.

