10.2. Definition of a Serious Adverse Event (SAE)

An SAE is a particular category of AE where the adverse outcome is serious. If an event is not an AE per definition above, then it cannot be an SAE even if serious conditions are met.

A serious adverse event is any untoward medical occurrence at any dose that:

- **Results in death**
- **Is life-threatening**
 - The term 'life-threatening' in the definition of 'serious' refers to an event in which the participant was at risk of death at the time of the event. It does not refer to an event, which hypothetically might have caused death, if it were more severe.
- **Requires inpatient hospitalization or prolongation of existing hospitalization**
 - In general, hospitalization signifies that the participant has been detained (usually involving at least an overnight stay) at the hospital or emergency ward for observation and/or treatment that would not have been appropriate in the physician's office or outpatient setting. Complications that occur during hospitalization are AEs. If a complication prolongs hospitalization or fulfills any other serious criteria, the event is serious. When in doubt as to whether hospitalization occurred, or was necessary, the AE should be considered serious.
 - Hospitalization for elective treatment of a pre-existing condition that did not worsen from baseline is not considered an AE.
- **Results in persistent or significant disability /incapacity**
 - The term disability means a substantial disruption of a person's ability to conduct normal life functions.

- This definition is not intended to include experiences of relatively minor medical significance such as an uncomplicated headache, nausea, vomiting, diarrhea, influenza, and accidental trauma (e.g., sprained ankle) which may interfere with or prevent everyday life functions but do not constitute a substantial disruption.

- **Results in congenital anomaly/birth defect**

- **Other situations:**

- Medical or scientific judgment should be exercised in deciding whether SAE reporting is appropriate in other situations, such as important medical events that may not be immediately life-threatening or result in death or hospitalization, but may jeopardize the participant or may require medical or surgical intervention to prevent one of the other outcomes listed in the above definition. These events should usually be considered serious.

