10.4. Time Period and Frequency for Collecting AE and SAE Information

All AEs, and therefore all SAEs, will be collected immediately after a participant provides consent to participate in the trial by the completion (signing) of the ICF and until 14 days following last administration of test product (or last study procedure). Medical occurrences that began before obtaining informed consent will be recorded in the source documentation as Medical History/Current Medical Conditions, not as AEs.

All SAEs will be recorded and reported to the Sponsor, or designee, immediately and under no circumstance should this exceed 24 hours. The PI, or designee, will submit any updated SAE data to the Sponsor within 24 hours of it being available.

The PI is not obligated to actively seek AEs or SAEs after the conclusion of study participation. However, if the PI learns of any SAE, including a death, at any time after a participant has been discharged from the study, and they consider the event to be reasonably related to the test product or study participation, the PI must promptly notify the Sponsor.

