10.6. Evaluating Adverse Events

Assessment of Intensity:

The PI, or medically qualified designee, will assess intensity for each AE reported during the study and will assign one of the following categories.

- **Mild:** An event that is easily tolerated by the participant, causing minimal discomfort and not interfering with everyday activities.
- **Moderate:** An event that is sufficiently discomforting to interfere with normal everyday activities
- **Severe:** An event that prevents normal everyday activities.

NOTE: An AE classified as **Severe** should not be confused with an SAE.

Severe is a category utilized to classify the intensity of an event; both non-serious AEs and SAEs can be classified as Severe. For example, a headache may be Severe (interferes significantly with the participant's usual function) but would not be classified as Serious unless it met one of the criteria for an SAE, as described above (Section 1.2.2.). An event is defined as 'serious' when it meets at least 1 of the pre-defined outcomes as described in Section 1.2.2., not when it is classified as Severe.

Assessment of Causality

Causality is one of the criteria used to determine regulatory reporting requirements. For each AE (serious and non-serious), the PI, or medically qualified designee, must provide an assessment of causality in the AE-specific source documentation and, for SAEs, on the SAE form.

The PI, or medically qualified designee, will use clinical judgment to determine causality, having also consulted the Safety Statement provided by the Sponsor for this study. Alternative causes, such as underlying disease(s), concomitant therapy, other risk factors and the temporal relationship of the event to the test product will also be taken into consideration and investigated.

There may be situations where an SAE has occurred, and the PI has minimal information to include in the initial report to GSK CH. The PI is required to make an assessment of causality prior to the initial transmission of the SAE form to GSK CH; they may change their opinion of causality in light of follow-up information and send an SAE follow-up report with the updated causality assessment.

Relationship to Test Material

The relationship or association of the AE to test product will be characterized as Unlikely, Possible or Probable (Table 10).

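### The general AE definition in Section 10.1 omits study procedures and the period before product, and Section 10.2 turns that omission into a bar on SAE status, in conflict with collection from consent

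*Combined protocol and SAP*

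**What the plan says.** **Definition.** Section 10.1: "An AE is any untoward medical occurrence in a clinical study participant, temporally associated with the use of a test product". The next sentence of 10.1 restates the definition with the same link to product use.

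**SAE condition.** Section 10.2: "If an event is not an AE per definition above, then it cannot be an SAE even if serious conditions are met".

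**Collection period.** Section 10.4: "All AEs, and therefore all SAEs, will be collected immediately after a participant provides consent to participate in the trial". Collection ends 14 days after the last product or the last study procedure. Only occurrences that began before consent go to medical history. Table 4 marks AE monitoring on Days 1, 2 and 3. Section 7.2.1 has AEs recorded at the Day 2 visit, before product is applied, and again when a paused participant returns.

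**Order of interventions.** UV doses go to an unprotected site on Day 1 (Sections 4.0 and 7.1.2, Table 4). The SPF standard and test products are first applied on Day 2 (Table 4, Section 7.2.2), or later, because "participants may leave the study site after MEDuI determination and return up to 1 week later to resume study procedures". Participants whose MEDuI cannot be determined are discontinued without receiving product.

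**Procedure-related events.** Section 10.0 requires follow-up of "AEs considered to be test product (or study procedure) related", and Section 10.5 has a similar duty. So the plan expects some AEs to arise from a procedure.

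**The concern.** The definition controls reporting. Section 10.0 makes the investigator responsible for events that meet the definition of an AE or SAE, and the 24-hour duty in Sections 10.4 and 10.5 attaches to SAEs. If an event cannot be an AE until a product has been used, the collection period from consent to first application has little in it by definition.

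That period contains the first UV exposure, and Section 10.3 itself lists the effects that UV may cause. At stake is whether a serious event in that interval, such as a collapse or a hospital admission the evening after Day 1 irradiation, is reportable. Site staff following Section 10.4 and site staff following Sections 10.1 and 10.2 would reach different answers.

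**Working it through.** The plan gives no figure to reproduce. The check compares the sections and works out the length of the affected period.

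**Step 1: length of the period before product**

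| Schedule | Inputs | Day 1 UV to first product |
|---|---|---|
| Standard | Evaluation 16 to 24 h after UV (7.1.2, 7.2.1), product at the same visit (Table 4) | about 16 to 24 h |
| Full pause | 24 h + 7 days (7.2.1) | 1 + 7 = about 8 days |
| Discontinued at MEDuI | No product given (7.2.1) | whole participation |

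A full pause puts product on Day 9 and final evaluation on Day 10, whereas Section 4.0 expects the study to last 3 to 8 days. If final evaluation must fall by Day 8, product is applied by Day 7, and the longest interval is 7 − 1 = 6 days. All of these intervals lie inside the 10.4 collection period.

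**Step 2: follow one event through the text.** Take a hospital admission for an event away from the back, after Day 1 UV and before product.

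1. Section 10.4: it began after consent, so it is not medical history, and it is within the collection period.
2. Section 10.1: no product has been used, so the association in time required by both sentences of the definition is absent. The listed examples for exacerbations and for new conditions also refer to the time after product administration.
3. Section 10.2: not being an AE, it cannot be an SAE, although hospitalization is a seriousness criterion.
4. Sections 10.4 and 10.5: not being an SAE, it carries no 24-hour duty.

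The event is therefore neither medical history nor an AE.

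**Step 3: look for routes that need no product**

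- The first listed example in 10.1 makes an unexpected reaction within a test site an AE if Table 8 cannot fully describe it. The Day 1 MEDuI site is one of the test sites (Section 4.0), so this route is open before product.
- Section 10.3 makes a UV effect an AE if it is highly exacerbated and leads to discontinuation. This also needs no product.
- The laboratory and safety-assessment example in 10.1 is not strictly limited to the time after product. Table 4 schedules no such tests, and the example concerns abnormal findings, not clinical events in general.

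**Step 4: what remains.** Two kinds of pre-product event have no route:

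- events away from the test site;
- effects on the 10.3 expected UV list that are severe but do not lead to discontinuation. Section 10.3 removes these expressly, so a change to 10.1 alone would not restore them.

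**The case against.** The strongest reply is that the intended handling is clear. Collection starts at consent, only pre-consent occurrences are medical history, Table 4 monitors AEs on Day 1, and Section 7.2.1 records AEs before product. Sections 10.0 and 10.5 speak of procedure-related AEs. Site staff following these would probably record a pre-product event, so the fault is one of drafting and no capture procedure is missing. That stands, and it limits the practical risk. It does not remove the conflict: those passages presuppose an AE and do not widen the definition, while 10.2 expressly makes the definition decisive. A loose reading, in which any event during a product study is associated in time with product use, fails for participants who never receive product.

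Several stronger readings are tempting but not supported:

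- *That no pre-product event can be an AE or SAE.* The two routes in 10.1 and 10.3 show otherwise.
- *That procedure-related AEs have nothing to trigger follow-up.* Section 10.7 follows all AEs, serious or not, whatever their cause. Section 10.5 lists relationship to a study procedure, where appropriate, among the essential SAE form items.
- *That an event caused by UV or by the SPF standard would be rated Unlikely.* The 10.6 scale is worded for test product, but its heading refers to test material, a term that Table 4 uses for the standard as well. Table 10 reserves Unlikely for a time relation that makes a link improbable. After Day 2 application, Possible could apply, and 10.6 counts that as related.
- *That half or more of the safety window is lost.* Elapsed time to the last visit gives 1/2 = 50% and 8/9 = 89%, but this omits the 14 days of follow-up. Counted to 14 days after product, the shares are 1/(1 + 14) = 7% and 8/(8 + 14) = 36%. None of these measures how many events would be missed.

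**Conclusion.** The concern holds as an internal conflict in the safety-reporting rules. Sections 10.1 and 10.2, read as written, cannot be followed together with Section 10.4, Table 4 and Section 7.2.1.

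Its extent is limited to pre-product events away from the test site and severe UV effects on the 10.3 list that do not lead to discontinuation. The exposed period is about 16 to 24 hours, up to about 8 days with the full pause, and the whole participation of anyone discontinued at MEDuI. Serious events of this kind should be rare. The documents give no rate, so no expected number can be stated.

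The conclusion assumes that association in time with product use means at or after application, which the wording of the 10.1 examples supports. It does not affect the SPF analysis, and the documents do not show that procedure-related AEs go without follow-up or that causality is misrated. The correction should be made because the rule gives a wrong result as written and is easily repaired.

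**What to change.** 1. Amend both sentences of the 10.1 definition so that the event may be associated in time with a test product, the SPF standard, or any study procedure including UV exposure, from signing of the ICF onward. The SPF standard needs naming because Section 3.0 lists it apart from the three test products.
2. Reconcile Sections 10.2 and 10.3 with 10.4 and Table 4. With 10.1 amended, the condition in 10.2 can stay. Section 10.3 should state how an effect on its expected UV list is classified when it meets a seriousness criterion but does not lead to discontinuation.
3. Optionally, add one field for relationship to study procedure to the record of every AE, matching the item that Section 10.5 already lists for the SAE form. Separate ratings for each product are not needed.

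The cost is a short protocol amendment, slightly more AE recording and, if the third step is taken, one extra field. Visits and procedures do not change.
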